6.3.8 Exposure to Treatment

The ongoing immunosuppressive treatments:

- Everolimus
- Cyclosporine (Control)
- Tacrolimus (Control)
- Prednisolone
- Mycophenolate mofetile (MMF)

will be presented by a frequency table.

The dose rate, daily dose registered in the Immunosuppressive Medication CRF-page at 5-7-years follow-up visit/time registered in the Immunosuppressive Medication CRF-page at 5-7-years follow-up visit, that was consumed by each patient will be presented in a summary table from end of main study until the 5-7-years follow-up visit. If start date is missing, end date of main study will be used (see Section 6.6).

The observed trough blood levels for Cyclosporine, Everolimus and Tacrolimus for the 5-7-years follow-up visit will be presented in a summary table.

The safety set, ITT, PPS and extended PPS population will be used and presented by treatment group and in total.

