4.2 Treatments

After randomization in the main study patients in Group A received an immunosuppressive regimen consisting of CsA, MMF and corticosteroids in both study periods. Patients in Group B commenced on an immunosuppressive regimen consisting of low dose everolimus and CsA, MMF and corticosteroids in period 1. In period 2 the patients were subjected to abrupt and complete CNI withdrawal, to a CNI free immunosuppressive regimen consisting of everolimus, MMF and corticosteroids.

After completion of the main study (12-months), most of the patients continued on the same immunosuppression. However, patients might have switched to alternative immunosuppressive drugs between Month 12 in the main study, the 3-year follow-up visit, and the 5 to 7-year follow-up visit.

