4.3 Efficacy assessments

The assessments to be performed at the 5 to 7-year follow-up visit are presented in Table 1. The same clinical methods/investigations as used for the 12-month assessments (Visit 11) and the 3-year follow-up will be used at the 5 to 7-year follow-up visit. Data from the main study and from the 3 year follow-up visit will also be used.

• Table 1 Assessment Schedule

Visit	Follow-up
Time after randomization	5 to 7 years
Informed consent	X
Baseline data	X
Concomitant therapy	X
Immunosuppressive therapy	X
12-led ECG	X
Vital signs	X
Echocardiography	X
Quality of life	X
IVUS ^{1,2}	X
Laboratory test hematology/biochemistry ³	X
Laboratory test/lipid profile ⁴	X
Urinalysis ⁵	X
██████████	██████████
mGFR	X
Drug concentration trough levels:	
CsA	X
Tacrolimus	X
Everolimus	X
Drug daily doses:	
CsA	X
Tacrolimus	X
Everolimus	X
Corticosteroids	X
MMF	X
AEs	X
SAEs	X

ECG, electrocardiogram; IVUS, intravascular ultrasound; ██████████; mGFR, measured glomerular filtration rate; CsA, cyclosporine; MMF, mycophenolate mofetil; AEs, adverse events; SAEs, serious adverse events

1. Measurements of microcirculation to be performed in connection with routine coronary angiography prior to IVUS examination (optional)
2. If IVUS is not performed as part of the assessments made at the follow-up study visit 5 or 6 years after transplantation IVUS may be collected at the subsequent regular annual routine visit
3. Hematology: hemoglobin, leukocytes, thrombocytes. Biochemistry: ASAT, ALAT, Urea, Creatinine, Uric acid, Sodium, Potassium, Albumin
4. Laboratory tests/Lipid profile: Total cholesterol, LDL-cholesterol, HDL-cholesterol, triglycerides, HbA1c, NT-proBNP, Troponin T, CRP
5. Urinalysis: Albumin/creatinine ratio

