4.3.2 Immunosuppressive Medication and Other Concomitant Medications

Present (at the time of the 5 to 7-year follow-up visit) immunosuppressive treatment (everolimus, CsA/tacrolimus, MMF, and corticosteroids [i.e. prednisolone]) including daily dose, information on start and/or stop of immunosuppressive treatment since the end of the original study and reasons for stopping/starting the immunosuppressive drugs will be collected. Present concomitant medications including indication and route of administration will also be collected.

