6.6 Handling of Dropouts and Missing Data

Outliers will be included in summary tables, and will not be handled separately.

[REDACTED]

[figure not shown]

Exposure of immunosuppressive treatments: If start date and/or end date is incomplete after Data Management processing, the following will be assigned for the missing **start** date:

- if no field is available: Month 12 (Visit 11) date of main study will be imputed
- if only the year is available: Day “01” and month of “July” will be imputed
- if the month and year are available: Day “15” will be imputed
- if start date is before transplantation date (Visit 2) will be imputed

The following will be assigned for the missing **end** date:

- if no field is available, i.e. the treatment is ongoing: 5-7-years follow-up date will be imputed
- if only the year is available: Day “01” and month of “July” will be imputed
- if the month and year are available: Day “15” will be imputed

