14.3 SAFETY DATA

(Safety presentations will be based on the Safety set if not other is stated below)

- 14.3.1.x Summary of Adverse Events
- 14.3.1.x Adverse Events by System Organ Class and Preferred term
- 14.3.1.x Summary of Serious Adverse Events
- 14.3.1.x Serious Adverse Events by System Organ Class and Preferred term
- 14.3.2 Listings of Deaths, Other Serious and Significant Adverse Events
- (14.3.3 *this title is reserved for narratives*)
- 14.3.4.x Abnormal Laboratory Value Listing (low and high, if reference values available)
- 14.3.4.x Other Relevant Laboratory Analyses:
 - Clinical chemistry/Biochemistry (summary statistics for observed values and change from baseline by treatment group and total values)
 - Lipid profile (summary statistics for observed values and change from baseline by treatment group and total values)
 - Hematology (summary statistics for observed values and change from baseline by treatment group and total values)
 - Urinalysis (summary statistics for observed values and change from baseline by treatment group and total values)
 - Shift Tables Clinical chemistry/Biochemistry
 - Shift Tables Lipid profile
 - Shift Tables Hematology
 - Shift Tables Urinalysis
- 14.3.5.x Extent of Exposure (Safety set, ITT, PPS, extended PPS)
 - Ongoing Immunosuppressive Treatments at 5-7-years Follow-Up (frequency table)
 - Dose Rate of Immunosuppressive Treatments from the End of the Main Study to the 5-7-years Follow-Up Visit (summary statistics)
 - Trough Blood Levels at 5-7-years Follow-Up (summary statistics for observed values)
- 14.3.6 Vital signs (summary statistics for observed values and change from pre-transplantation by treatment group and in total)
- 14.3.7.x ECG (summary statistics for observed values)
 - Shift ECG for Type of Rhythm

14.3.8.x Cardiac Rejections (frequency table by treatment group)

- Number of patients with at least one cardiac rejection (grade I-III): cellular, humoral or mixed (for three periods: during the main study, between main study to 3-years follow-up and between 3-years follow-up to 5-7-years follow-up)
- Total number of cardiac rejection grade I-III (cellular, humoral or mixed, for three periods: during the main study, between main study to 3-years follow-up and between 3-years follow-up to 5-7-years follow-up)

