14.3.9 Concomitant Medication at 5-7-years Follow-Up Visit

7.2 Graphs (Section 14.2-14.3 in ICH E3)

None

7.3 Listings of Individual Patient Data and other Information to be Produced for the Clinical Study Report (Sections 16.1 and 16.2 according to ICH E3)

(Listing numbers refer to Appendix number in ICH E3. CRF check questions/reminders will not be listed.)

- 16.1.7 Randomisation Scheme (*Copy of List, included in CSR for 12 Months*)
- 16.2.1.x Discontinued Patients, Reason for Discontinuation (from 3-years follow-up to 5-7 follow-up visit)
- 16.2.1.x Visit Dates and Other Important Dates
- 16.2.1.x *Study Termination – Not Applicable*
- 16.2.2 Protocol Deviations
- 16.2.3.x Patients Excluded from the Efficacy Analysis (Evaluable, Reason for Evaluable Classification)
- 16.2.3.x Treatment Allocation and Evaluable for All Patients
- 16.2.4.x Demographic Data
- 16.2.4.x Inclusion Criteria Not Met and Exclusion Criteria Met
- 16.2.5 Compliance and/or Drug Concentration Data
 - Immunosuppressive Medications
 - Immunosuppressive Level
- 16.2.6 Individual Efficacy Response Data
 - mGFR (mL/min/1.73m²)
 - IVUS (performed yes/no and date)
 - Echocardiography

- SF-36
- EQ-5D
- BDI form
- [REDACTED]

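### SAP 6.3.8 writes the dose rate as a daily dose divided by time; taken literally, the same dose scores lower the longer it has been taken

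*SAP*

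**What the plan says.** SAP 6.3.8 gives the only definition of the dose rate in the visible text: "daily dose registered in the Immunosuppressive Medication CRF-page at 5-7-years follow-up visit/time registered in the Immunosuppressive Medication CRF-page at 5-7-years follow-up visit". The sentence goes on to describe this as the rate "that was consumed by each patient will be presented in a summary table from end of main study until the 5-7-years follow-up visit". Appendix 1 of the SAP, under 14.3.5.x, lists the output as "Dose Rate of Immunosuppressive Treatments from the End of the Main Study to the 5-7-years Follow-Up Visit (summary statistics") and adds no formula or unit. The table is planned for the safety set, ITT, PPS and extended PPS.

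SAP 6.6 has rules for incomplete start and end dates of immunosuppressive treatment. A start date with no field available becomes the Month 12 (Visit 11) date, and an ongoing treatment ends at the follow-up visit. The time in the expression is therefore a duration.

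On the data side, Protocol Table 1 lists "Drug daily doses" at the follow-up visit. Protocol 4.3.2 says that present treatment will be recorded, "including daily dose, information on start and/or stop of immunosuppressive treatment since the end of the original study".

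**The concern.** The numerator is already a rate. A second division by time gives a quantity with no clear meaning as exposure. It also moves the wrong way: with the dose held fixed, longer treatment gives a smaller number. The follow-up visit falls at 5, 6 or 7 years by design, so duration differs between patients even when treatment never changed.

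At stake is one descriptive table. It is, however, the only planned summary of dose that claims to cover the whole interval from the end of the main study to the visit. The frequency table and the trough levels describe the visit only. In a study of long-term cyclosporine elimination, readers may use this table to judge how much of each drug was taken. A programmer who follows the sentence literally would produce figures that cannot be read that way.

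**Working it through.** The documents state no dose-rate value, so there is no figure to reproduce. The check is of the definition itself.

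**Inputs**
- Visit at 5, 6 or 7 years (SAP section 1).
- Summary period from the end of the main study, Month 12, to that visit (SAP 6.3.8).
- Time is a duration between start and end dates (SAP 6.6).
- A constant daily dose D, kept as a symbol; it cancels from every ratio.

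**Step 1. The expression as written.** R = D / T, in dose per day per year.

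| Visit | T from Month 12 | R | T from transplantation | R |
|---|---|---|---|---|
| 5 years | 5 − 1 = 4 | D/4 = 0.250D | 5 | D/5 = 0.200D |
| 6 years | 6 − 1 = 5 | D/5 = 0.200D | 6 | D/6 = 0.167D |
| 7 years | 7 − 1 = 6 | D/6 = 0.167D | 7 | D/7 = 0.143D |

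Ratio of the 5-year to the 7-year value: (1/4)/(1/6) = 1.5 from Month 12, and (1/5)/(1/7) = 1.4 from transplantation. Put the other way, the 7-year value is 33% or 29% lower for the same dose. Month 12 is the window that 6.3.8 states. Transplantation is shown because 6.6 also mentions it as a date that may be imputed.

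**Step 2. Amount over time, for comparison.** (D × T) / T = D at every visit, so the spread disappears.

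**Step 3. Different doses can score the same.** 1.5D for 6 years gives 1.5D/6 = 0.25D. D for 4 years gives D/4 = 0.25D.

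**Step 4. Shorter use.** Take an assumed patient with 2 years on a drug at a 6-year visit (window 5 years), and compare with the same dose for the full window.

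| Reading | 2 years on drug | Full window | Ratio |
|---|---|---|---|
| As written, D / time on drug | D/2 = 0.50D | D/5 = 0.20D | 2.5 |
| Amount / time on drug | 2D/2 = 1.00D | 5D/5 = 1.00D | 1.0 |
| Amount / window | 2D/5 = 0.40D | 5D/5 = 1.00D | 0.4 |

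The three readings disagree even in direction. The 2-year duration is illustrative; the documents do not say how many patients had short use.

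**Step 5. What the described data allow.** With one present dose per drug, amount over time on drug is (D × T)/T = D. Time cancels and the result is simply the current dose.

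**The case against.** The strongest reply is that 6.3.8 is prose and not a displayed formula. The label dose rate, the word consumed and the stated period all point to amount over time, and the slash may be loose shorthand. That is a fair reading, and the programmed table might be sensible. But the text contains no amount, does not say whether the divisor is time on drug or the whole window, and gives no unit. Step 4 shows that this choice matters.

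A second reply is that little depends on the table. This stands. It feeds no test, and individual medication records and drug levels are listed under "16.2.5 Compliance and/or Drug Concentration Data", so the summary could be checked against them.

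Three stronger readings are tempting, and the documents do not support them:
- A reader might infer that for most patients the value would reflect visit year alone, because Protocol 4.2 says "most of the patients continued on the same immunosuppression". That statement concerns the regimen, not the dose. Doses may differ between patients and may change, and SAP 4.1 says only that some continued and some switched.
- A reader might infer that the comparison of arms is biased. That would need visit timing, or the number and duration of switches, to differ by arm. The documents give neither.
- A reader might infer that the date rules in SAP 6.6 are also defective, because the bullet on start dates before transplantation reads as incomplete. Part of 6.6 is redacted, and the bullet may only have lost a comma, so it is not part of this point.

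**Conclusion.** The definition is wrong as written, and the point is minor. Followed literally, the dose rate is inversely proportional to duration. An unchanged dose differs 1.5-fold between 5- and 7-year visits with time from Month 12, or 1.4-fold from transplantation, and shorter use scores higher. These figures assume whole-year visit timing, continuous use and a constant dose. How far the real table would be distorted cannot be worked out, because the documents do not give the distribution of visit years, doses or durations.

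The effect stops at the exposure table in 14.3.5.x. Nothing supports extending it to the primary mGFR result, the analysis sets, the trough levels or the frequency table.

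**What to change.** In SAP 6.3.8, replace the ratio with two variables summarised separately for each drug: current daily dose, and time on drug between Visit 11 and the follow-up visit, both with units. This uses only what Protocol 4.3.2 says is collected. A drug stopped before the visit would contribute time but no current dose, so the number of patients behind each summary should be shown.

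If the CRF page, which is not among the documents, holds dated dose periods, report instead the time-weighted mean daily dose: sum(daily dose × days at that dose) / sum(days on drug). Align the table title in Appendix 1 with whichever is chosen.

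The cost is one sentence, a table title and a small change to the derivation code before database lock. The downside is that, if only the present dose is held, dose changes between visits remain invisible, and the table should say so.

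### The exposure table claims a dose consumed since Month 12, but the protocol describes daily dose only for treatment being taken at the 5-7-year visit

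*SAP*

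**What the plan says.** SAP 6.3.8 builds the dose rate from a single source: "daily dose registered in the Immunosuppressive Medication CRF-page at 5-7-years follow-up visit/time registered in the Immunosuppressive Medication CRF-page at 5-7-years follow-up visit". It describes the result as the rate "that was consumed by each patient will be presented in a summary table from end of main study until the 5-7-years follow-up visit". The table list in SAP Appendix 1 (14.3.5) puts the same period in the title: "Dose Rate of Immunosuppressive Treatments from the End of the Main Study to the 5-7-years Follow-Up Visit".

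Protocol 4.3.2 says what is recorded. Daily dose belongs to current treatment: "Present (at the time of the 5 to 7-year follow-up visit) immunosuppressive treatment (everolimus, CsA/tacrolimus, MMF, and corticosteroids [i.e. prednisolone]) including daily dose". For the years since the main study the protocol adds "information on start and/or stop of immunosuppressive treatment since the end of the original study and reasons for stopping/starting the immunosuppressive drugs". In Protocol 4.3, Table 1 has a block headed "Drug daily doses", marked for the one follow-up visit.

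SAP 6.6 has date rules for this exposure calculation. When nothing is recorded for a start date, the rule is: "if no field is available: Month 12 (Visit 11) date of main study will be imputed". The same section has rules for incomplete end dates and reads a blank end date as treatment still in progress.

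**The concern.** The period that the table claims is longer than the period for which the protocol describes doses. A current daily dose is one point in time. The word consumed, together with a window starting at Month 12, tells the reader that it represents what the patient took over several years.

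This matters because the trial asks whether eliminating CsA early protects the kidney in the long run. Both documents accept that patients may have changed drugs after Month 12 (Protocol 4.2, SAP 4.1). Anyone interpreting the mGFR comparison will want to know how much CNI and everolimus each arm received in between. The other two exposure summaries in SAP 6.3.8, ongoing treatments and trough levels, are both snapshots at the visit. The dose-rate table is the only by-arm summary in the readable text that claims to cover the interval, so readers will rely on it for that.

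**Working it through.** The plan states no exposure figure, so there is none to reproduce. The check compares what the table claims with what is collected, and then sizes the gap under stated assumptions.

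**Length of the window.** It runs from Month 12 to the visit, so length = visit year − 1, taking visits at whole years:
- 5-year visit: 5 − 1 = 4 years
- 6-year visit: 6 − 1 = 5 years
- 7-year visit: 7 − 1 = 6 years

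This is the most that one visit dose can stand for. It applies to a drug taken since Month 12, or to one whose start date is wholly missing and is therefore set to Month 12. A drug started later covers less time.

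**What is held for each part of the window, according to Protocol 4.3.2.**
- Drug in use at the visit: current daily dose and start information, but no history of dose changes.
- Drug stopped before the visit: start and stop information and reasons, but no dose mentioned.

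**Visit dose against the time average, for a drug still in use.** Let r be the earlier dose divided by the visit dose, and f the share of the time on drug spent at the earlier dose. Both are assumptions, because the documents give no doses. In units of the visit dose, the time-weighted mean is f × r + (1 − f). The visit dose as a fraction of the true mean is 1 / [f × r + (1 − f)].

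| r | f = 0.25 | f = 0.50 | f = 0.75 |
|---|---|---|---|
| 2.0 | 1/1.25 = 0.80 | 1/1.50 = 0.67 | 1/1.75 = 0.57 |
| 1.5 | 1/1.125 = 0.89 | 1/1.25 = 0.80 | 1/1.375 = 0.73 |
| 0.5 | 1/0.875 = 1.14 | 1/0.75 = 1.33 | 1/0.625 = 1.60 |

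A dose halved midway (r = 2, f = 0.5) is shown at 67% of its time average. A dose doubled midway (r = 0.5, f = 0.5) is shown at 133%. The sign depends on whether doses fell or rose.

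**Stopped courses.** Take an assumed CNI course from Month 12 that ended two years later. Its dates give the share of the window on drug: 2/4 = 50% for a 5-year visit and 2/6 = 33% for a 7-year visit. Its dose contribution cannot be derived from the protocol text, because no dose is described for it. Time on drug can therefore be calculated from what is collected, whereas dose over the interval cannot, unless the CRF holds more than the protocol says.

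SAP 6.3.8 also divides a daily dose by a time. That is a separate question, and nothing here depends on it.

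**The case against.** The strongest reply is that the CRF page is not among the documents. If each line of it holds drug, start, stop and daily dose, then stopped courses and dose changes are captured and the table can be produced as described. Protocol 4.3.2 is one compressed sentence and Table 1 is a visit checklist, so neither proves that earlier doses are absent. This stands as a limit on the point: the gap is in what the documents describe, and the CRF may be fuller.

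A reader might go further and infer that stopped drugs disappear from the table. The documents do not support that. Protocol 4.3.2 collects stops, and the partial end-date rules in SAP 6.6 make sense only if courses that ended before the visit enter the calculation. What is undefined is the dose attached to them.

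A reader might also infer that the arms would look more cleanly separated than they were. That does not follow either. CNI stopped in the control arm would act in the opposite direction to CNI stopped in the everolimus arm, doses may have risen or fallen, and no switch counts are given.

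Two further replies are correct but do not settle the matter. Individual medications are to be listed (Appendix 1, 16.2.5), but a listing is not a summary by arm. Protocol 4.3 says that main-study and 3-year data will be used, but the dose-rate definition names only the 5-7-year CRF page.

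**Conclusion.** The point holds as a mismatch between the claim and the described data. The table promises dose over an interval of up to 4 to 6 years, whereas the protocol describes dose at its end only. For a drug still in use, the visit dose is 0.57 to 0.89 of the time average if the earlier dose was 1.5 to 2 times higher for 25% to 75% of the time. It is 1.14 to 1.60 of that average if the earlier dose was half as high. These ranges illustrate assumed patterns and do not estimate what happened in the trial.

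The consequence is limited. The table is descriptive. The primary ANCOVA does not use it, and membership of the PPS and extended PPS depends on treatment at the visit, not on this dose rate. The change is still worth making, because the table informs how the mGFR result is read in a trial with acknowledged switching, and a better summary can be built from dates already collected.

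**What to change.** 1. Retitle the dose table as daily dose at the 5-7-year visit among users of each drug, and drop the wording about consumption since the main study. Add Month 12 and 3-year doses where they are held; the documents do not confirm that 3-year doses were recorded.
2. Add a by-arm table of time on any CNI and time on everolimus, each as a percentage of the interval from Month 12 to the visit. Derive it from start and stop dates, count courses that ended before the visit, and show how many dates were imputed under SAP 6.6.
3. If the CRF does record a dose for each treatment period, say so in SAP 6.3.8 and define instead a time-weighted mean daily dose: the sum of dose × days over all periods, divided by the days in the interval.

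The cost is SAP wording, one retitled table and one new one. The time-on-drug table needs no new patient data. The downside is slightly more table work, and the single interval dose-rate figure is given up unless per-period doses exist.
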